16.3 Analysis of Outcome Measures

Key aspects of the analysis methods to be utilised are detailed below and the statistical analysis plan will provide details of the selection of subjects to be included in each analysis in addition to procedures accounting for missing, unused or spurious data.

Primary Outcomes

Re-excision following initial procedure

Once all patients have undergone surgery the proportion of patients requiring re-excision will be compared between the trial arms. A 2-sided 95% confidence interval around the difference in proportions will be calculated. If the upper bound of the confidence interval is below 10 then non-inferiority will be declared. If non-inferiority is declared then a pre-specified but unpowered analysis of superiority will also be undertaken, to investigate whether superiority has also been demonstrated.

Local recurrence free survival time for VAE

The point estimate for local recurrence free survival at 5 years will be calculated with 2-sided 95% confidence interval using the Kaplan-Meier method. No hypothesis testing will be performed. This will be interpreted both with reference to the same rate calculated for the surgery arm of the trial and in relation to the undesirable local recurrence rate of 97%. Sensitivity analysis will be conducted utilising exact methods for calculating the proportion of recurrence at 5 years to explore the appropriateness of the Kaplan-Meier method.

Secondary Outcomes

Time to ipsilateral breast cancer recurrence, time to development of contralateral invasive breast cancer and overall survival will be analysed as per local recurrence free survival time above. Complications arising from surgery or VAE will be reported descriptively for both treatment arms (see Appendix 4 for complications and definitions). No hypothesis testing will be conducted.

QoL will be analysed using standardised area under the curve and appropriate repeated measures modelling techniques to compare treatment arms.

Page 31 of 49

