1.2.2 Justification for design

It is appropriate to address the issue of overtreatment of screen-detected early breast cancer through a prospective randomised trial. In order for this trial to be practice-changing, it will be necessary to demonstrate that not only is there an acceptable local recurrence (LR) risk associated with VAE followed by radiotherapy (RT) and endocrine therapy (ET), but also that there is no excess requirement for additional procedures in the case of radiologically-determined incomplete excision. It is possible there may be fragments of microscopic disease remaining in the breast following VAE, but what is important is not their presence, but their impact on long-term clinical outcomes (LR in this context). It is well-recognised that following surgical excision a negative pathological margin does not indicate no residual tumour within the breast²⁸, but rather that the residual disease burden is likely to be sufficiently low to be controlled by adjuvant therapy. The role of both RT and adjuvant systemic therapies in maintaining local disease control are well documented^{29,30}. Furthermore, a large Dutch cohort study demonstrated that omission of re-excision for focally involved margins (where microscopic foci of residual malignancy may be seen) was associated with a 5-year local recurrence rate of 2.9%, when whole-breast RT was given following surgery. Although this local recurrence rate was reduced by surgical re-excision, this did not impact 5-year disease free or overall survival³¹.

Consequently the study is designed with co-primary endpoints, to demonstrate non-inferiority of VAE in terms of requirements for a second procedure, and to demonstrate acceptable long-term local recurrence rates following VAE in these tumours.

Thus, the rationale for adjuvant therapies following breast surgery is based on the premise that there may be an undetected microscopic cancer burden likely to benefit from additional treatment, and this principle has underpinned the safe introduction of breast conserving therapy for early breast cancer.

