16.7 Power Calculations

The total number of patients to be recruited with an allocation ratio of 2:1 is 800 (533 VAE, 267 surgery). The total number of patients required for the re-excision comparison was 762³⁹ which has been inflated by 5%. This will ensure that we have sufficient patients for the single arm investigation into local recurrence rates with VAE, and allow for possible drop-outs. To ensure that the trial as a whole only has 5% alpha the significance level for each of the co-primary outcomes has been set at 2.5% with 90% power. The probability of success in both the surgery arm and the VAE arm is expected to be 80% (20% re-excision). The maximal acceptable difference between the two has been set at 10% which was defined as acceptable by PPI bearing in mind that this is salvageable by a second procedure and has no survival sequelae. The total number required for the local recurrence free survival outcome is 511⁴⁰ (VAE). This assumes that the expected survival probability at 5 years is 99%²⁵ and that an undesirable survival probability for VAE is 97% at 5 years. Allowing for 4 years recruitment and following all patients for a minimum of 3 years post randomisation.

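### Section 16.3 mislabels the recurrence threshold for co-primary 2 and gives no rule for clearing it, although Section 16.7 sizes that outcome as a test

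*Protocol*

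**What the plan says.** Section 1.2.2 makes the conclusion depend on two findings. For the trial to change practice, "it will be necessary to demonstrate that not only is there an acceptable local recurrence (LR) risk associated with VAE", and there must also be no excess of second procedures.

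Section 16.7 sizes both outcomes as tests: "the significance level for each of the co-primary outcomes has been set at 2.5% with 90% power". For local recurrence it takes 99% as the expected and 97% as the undesirable 5-year recurrence-free probability, and arrives at 511 VAE women. For re-excision it sets a maximal acceptable difference of 10%.

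Section 16.3 then describes the analyses.
- Re-excision: "A 2-sided 95% confidence interval around the difference in proportions will be calculated", followed by "If the upper bound of the confidence interval is below 10 then non-inferiority will be declared".
- Local recurrence after VAE: a Kaplan-Meier estimate at 5 years with a two-sided 95% interval. It adds "No hypothesis testing will be performed". The estimate is to be read alongside the surgery-arm rate and "in relation to the undesirable local recurrence rate of 97" per cent. An exact calculation of the 5-year proportion is planned as a sensitivity analysis.

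**The concern.** Two things in Section 16.3 do not fit Section 16.7.

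First, the threshold carries the wrong label. A 97% recurrence rate and a 97% recurrence-free probability are opposite quantities, and the error is in the section that governs interpretation.

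Second, and more important, a significance level and a power describe how often a stated rule gives the wrong or the right answer. Section 16.7 quotes both for local recurrence, but Section 16.3 rules out a test and puts no criterion in its place. Two readings are open: the estimate must exceed 97%, or the lower confidence limit must. They lead to very different standards of evidence for a claim about cancer recurrence after less surgery. If the choice is made once the data are known, the stated 2.5% and 90% no longer describe the trial.

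**Working it through.** **1. Reproduce the re-excision sample size.** Inputs from Section 16.7: 80% success in both arms, margin 0.10, 2:1 allocation, 2.5% level, 90% power. Taking the 2.5% as one-sided:

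n(surgery) = (1.960 + 1.282)² × (0.16 + 0.16/2) / 0.10² = 252.2, rounded up to 253.

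VAE = 506 and the total is 759, against 762 stated. 762 × 1.05 = 800.1, which matches 800. At one-sided 1.25% the total would be 894. So the margin is 10 percentage points, the level is one-sided 2.5%, and the two-sided 95% interval in Section 16.3 agrees with it. With 533 and 267 women, power is 91.5% and the interval half-width is 1.96 × √(0.16/533 + 0.16/267) = 5.9 points. VAE passes if the observed excess is below about 4.1 points.

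**2. Reproduce the local recurrence sample size.** An exact one-sample binomial test of 97% against 99% recurrence-free, one-sided 2.5% and 90% power, needs 522 women. Time-to-event and normal-approximation variants at one-sided 2.5%, with 4 years' accrual and 3 years' minimum follow-up, mostly give about 474 to 540. The stated 511 lies in this range, though no variant tried returned it exactly. It makes sense only if 97% is the recurrence-free probability.

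**3. Compare the two possible rules.** Assumptions: 533 VAE women, complete 5-year data, exact binomial, Clopper-Pearson limits.

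| Rule | Boundary check | Most recurrences allowed | Success if true recurrence is 1% | Success if true recurrence is 3% |
|---|---|---|---|---|
| Lower 95% limit above 97% | upper limit for recurrence is 2.94% with 8 events, 3.18% with 9 | 8 | 90.9% | 2.1% |
| Point estimate above 97% | 15/533 = 2.81%; 16/533 = 3.002% | 15 | over 99.9% | 46.6% |

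Only the first rule is close to the stated 2.5% and 90%. The two rules disagree for 9 to 15 recurrences. If true recurrence is 3%, such a result has probability 46.6% − 2.1% = 44.5%. With 511 women the limits are 7 and 15 recurrences, and false success is 1.4% and 53.4%.

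**4. Check the confidence-limit rule under the planned follow-up.** Section 16.6 places the analysis 3 months after every patient has completed 3 years of mammography, so with 4 years' recruitment many women will have less than 5 years' follow-up. Simulation assumptions: 533 women, uniform accrual over 4 years, analysis 3.25 years after the last randomisation, exponential recurrence, no dropout. Separate runs agree within about one percentage point.

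| Kaplan-Meier 95% limit | False success at 3% recurrence | Power at 1% recurrence |
|---|---|---|
| Plain or log-transformed Greenwood | about 5.6% | about 95% |
| Log-log | 1.5% to 1.8% | 82% to 83% |

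Neither type delivers 2.5% and 90% together, so the interval type belongs in the rule.

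**The case against.** The strongest defence is that both slips can be resolved from the protocol. Section 16.7 states the 97% correctly, and no analyst would accept 96% recurrence. Estimation with an interval is a legitimate way to report a rare event, and further detail may be in the SAP. The first part stands: the 97% label is an editorial error with a certain correction. The rest does not settle the matter. Section 16.3 leaves the selection of subjects and the handling of missing or spurious data to the SAP, but it states a success criterion for re-excision itself. The conflict between no testing and a 2.5% level with 90% power lies within the protocol.

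Three stronger readings are tempting, and the documents do not support them.

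- *The re-excision rule can never fail, because a difference in proportions is always below 10.* Section 16.7 gives the margin as 10%, and its sample size reproduces with 10 percentage points. The direction follows from testing non-inferiority of VAE on an adverse outcome with an upper bound. Only the unit and the direction of subtraction need to be written in.
- *Splitting alpha is an error, because both outcomes are required.* The stated aim is "To ensure that the trial as a whole only has 5% alpha". If both are required, the error is at most the 2.5% of one outcome, so 5% remains true as an upper bound. Removing the split would change no interval and no sample size.
- *The trial has only 81% power for its joint claim.* That figure multiplies two nominal 90% values under assumed independence. Section 16.7 claims 90% for each outcome and never jointly, and step 4 shows that the power for local recurrence depends on an interval type not yet chosen.

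Reading the VAE result alongside the surgery-arm rate is also no defect, provided that it stays descriptive.

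**Conclusion.** The point holds for co-primary 2. Section 16.3 labels a recurrence-free probability as a recurrence rate, and it withholds a success rule from an outcome that Section 16.7 sizes as a test and Section 1.2.2 makes necessary for the conclusion. The gap between the available rules is 8 against 15 recurrences among 533 women, with false success of 2.1% against 46.6% at 3% true recurrence. These counts assume complete 5-year data. Kaplan-Meier results under staggered follow-up would differ somewhat, but the two rules would still differ widely. Co-primary 1 can be decided as the protocol stands, so the trial's conclusion is left open by the missing rule for local recurrence and not by the two misprints. This should be settled before the local recurrence data are analysed.

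**What to change.** In Section 16.3:

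1. Replace the threshold with: *undesirable 5-year local recurrence-free survival of 97% (3% recurrence)*.
2. Replace the statement that nothing will be tested for co-primary 2 with: *local recurrence after VAE is acceptable if the lower limit of the two-sided 95% confidence interval for 5-year local recurrence-free survival in the VAE arm is above 97%*.
3. Name the interval type, for example log-log, and restate the error and power of the rule under the planned follow-up with the assumptions shown.
4. Keep the surgery-arm rate as descriptive context.
5. As an editorial correction for co-primary 1, write *10 percentage points (VAE minus surgery)*.

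If the sponsor prefers co-primary 2 to be purely descriptive, its significance level and power should come out of Section 16.7, and Section 1.2.2 could no longer say that acceptability will be demonstrated.

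The change is to wording only: no patients, visits or procedures are added. The cost is that the stated power for co-primary 2 may fall below 90% (to about 83% with log-log limits). Plain or log limits keep the power, but their false-success rate of about 5.6% exceeds the stated 2.5%.

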16.4 Planned Sub Group Analyses

No subgroup analyses are planned.

16.5 Planned Interim Analysis

No formal interim analysis is planned. Cumulating data will be reported to an independent data monitoring committee at 6, 12, 18 and 24 following trial opening and then annually, as required. Data presented will include trial recruitment and conduct, data completeness, compliance, safety and complications data relating to randomised allocation, subsequent procedures, radiotherapy, endocrine therapy and all adverse events. The DMC will also monitor local recurrence events to ensure that it does not exceed an acceptable threshold. The acceptable threshold has been set at 3% per year which was established in close consultation with the PPI members of the trial development group, and is set in recognition of the fact that local recurrence is not a life-threatening condition and is salvageable with further surgical treatment.

16.6 Planned Final Analyses

The final analysis of re-excision following initial procedure will be conducted 3 months following the completion of recruitment. This will ensure all patients have undergone randomised procedures and been assessed for re-excision. The analysis of complications arising from surgery or VAE will also be conducted at this point. Analysis of the local recurrence free survival and all remaining secondary outcomes will be conducted 3 months after all patients have completed 3 years of annual mammography following randomisation.

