2.2.2.2 Secondary outcome measures

- 1. Complications arising from surgery or VAE
- 2. Time to ipsilateral breast cancer recurrence
- 3. Time to development of contralateral invasive breast cancer
- 4. Overall survival time
- 5. Quality of life: will be assessed using the following tools:
 - o EORTC QLQ-C30 and BR23
 - o EuroQoL EQ-5D
 - o BREAST-Q (breast conserving therapy module)
- 6. Quality-adjusted life year (QALY)

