8.1.3 BREAST-Q (breast conserving therapy module)

The BREAST-Q is a patient-reported outcome instrument designed to evaluate outcomes among women undergoing different types of breast surgery and includes a BCT (breast conserving therapy) module appropriate to the patient population in this study³⁷. The BREAST-Q comprises two over-arching themes, which are patient satisfaction and health-related quality of life. Body image is an important concept for many women undergoing treatment for breast cancer, and it is possible that there may be differences in body image perception and satisfaction with breasts between the conventional surgery arm and the VAE arm, which is the rationale for utilising the BREAST-Q in this study.

	Time points (months from randomisation)						
Questionnaires	Baseline	6	12	24	36	48	60
EORTC QLQ-C30 & BR23	~	~	~		~		~
BREAST-Q	~		~	~	~	~	~
Euro-QoL EQ-5D	~	~	~	~	~	~	~

Table 2: Timeline for Quality of Life Questionnaires

With the exception of the baseline QoL questionnaires, which will be completed by the patient prior to randomisation, all other questionnaires will be distributed directly to the patients' home address by the SMALL Trial Office for completion at the designated time points.

Site research teams should inform the SMALL Trial Office immediately upon becoming aware of any changes to patient contact details by completing and returning the Change of Patient Contact Details Form.

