9.3 Analyses

The main analysis will be undertaken at completion of the project, using the data analyses from the trial. There will be two components to the analysis: a within trial analysis and a model-based analysis.

Model-based analysis - a preliminary modelling exercise will be carried out at the beginning of the study and will be populated and refined during the pilot to prepare for the end of trial analysis.

A decision analytic model will be used to allow the extrapolation of cost and effectiveness parameters beyond the data observed in the clinical trial (and to allow extrapolation to other settings). The model will, therefore, consider treatment over total disease duration and will include surgical treatments provided in the longer term. An individual sampling model (such as a Markov model) or similar model to ensure time to event can be analysed. A preliminary model-based analysis will be conducted during the initial months of the study, using all available data and highlighting areas of uncertainty to be targeted during the trial – this will be revisited during the pilot stage and draw upon follow-up data up to 18 months. This will utilise published data and assumptions to predict costs and benefits into the long-term. The analysis will then be repeated in the last 12 months of the study using the main trial and follow-up data, but still predicting costs and effects beyond the trial end.

Results of all economic analyses will be presented using cost-effectiveness acceptability curves to reflect sampling variation and uncertainties in the appropriate threshold cost-effectiveness value. We shall also use simple and probabilistic sensitivity analyses to explore the robustness of these results to plausible variations in key assumptions and variations in the analytical methods used, and to consider the broader issue of the generalisability of the results.

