15. END OF TRIAL DEFINITION

The end of trial will be 6 months after the last data capture, or the final analysis of predictive biomarkers, whichever is later. This will allow sufficient time for the completion of protocol procedures, data collection and data input.

The duration of time for which patient follow-up data will be collected is dependent on future funding arrangements. Current funding is secured for this to continue for 5 years after randomisation of each patient and further funding will be sought to continue this in the longer term.

The Trial Office will notify the main REC that the trial has ended and a summary of the clinical trial report will be provided within 12 months of the end of trial.

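### Section 16.6 sets the only planned quality-of-life analysis at 3 years' minimum follow-up, before the funded 48- and 60-month questionnaires of later recruits exist, and does not align the QALY with section 9.3

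*Protocol*

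**What the plan says.** Protocol section 16.6 (Planned Final Analyses) has two analysis times. The first, 3 months after recruitment closes, covers re-excision and one secondary outcome: "The analysis of complications arising from surgery or VAE will also be conducted at this point". The second covers everything else: "Analysis of the local recurrence free survival and all remaining secondary outcomes will be conducted 3 months after all patients have completed 3 years" (counted by yearly mammograms). Section 16 names no third time.

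Section 2.2.2.2 lists quality of life as secondary outcome 5 ("Quality of life: will be assessed using the following tools") and the QALY as secondary outcome 6. Both are therefore among the remaining secondary outcomes.

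The data run longer than that cut. In section 8.1.3, "Table 2: Timeline for Quality of Life Questionnaires" has all three instruments at 60 months. EQ-5D and BREAST-Q are also taken at 48 months. QLQ-C30/BR23 is not, so its last score before 60 months is at 36 months. On follow-up, section 15 says: "Current funding is secured for this to continue for 5 years after randomisation of each patient". Section 16.3 compares the arms on quality of life by standardised area under the curve (AUC) and repeated-measures models.

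Section 16.2.2 sends the QALY to the health economic analysis of section 9, and section 9.3 gives that analysis its own time: "The main analysis will be undertaken at completion of the project, using the data analyses from the trial".

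**The concern.** The 3-year cut is tied to mammography. The only reason the protocol gives for a 3-year minimum is the local recurrence calculation in section 16.7, and nothing links it to the questionnaires. Followed as written, section 16.6 runs the only planned quality-of-life analysis while many women have not reached their last one or two scheduled questionnaires. Those scores would still be collected, at funded cost and with effort from the women, but no analysis in section 16 would use them.

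The QALY has a related problem. Section 16.6, taken literally, puts it at the 3-year cut, while section 9.3 puts the analysis that uses it at the end of the project. Section 9.2 designs the resource-use collection to span five years from randomisation, so costs and QALYs for later recruits could not cover that period at the section 16.6 cut.

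**Working it through.** The protocol gives no figure for the share of women with a late score, so there is none to reproduce. The share follows from the calendar.

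**Inputs**
- Recruitment lasts 48 months (section 3).
- The second analysis comes 36 + 3 months after the last randomisation (section 16.6).
- N = 800 (section 16.7). Percentages are applied to women in the optional quality-of-life sub-study, assuming they accrue in the same pattern.
- The only accrual figure is 141 patients by month 18 (section 16.1.3, a progression criterion).
- Questionnaires are as in Table 2, with funded follow-up of 60 months per woman (section 15).

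**Calendar time of the analysis.** 48 + 36 + 3 = month 87 from opening. A score at m months can exist only for women randomised by month 87 − m: month 27 for the 60-month score and month 39 for the 48-month score. This counts the 3-month lag as follow-up.

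**Even accrual over 48 months**
- No 60-month score: 1 − 27/48 = 43.75%, or 350 per 800.
- No 48-month score: 1 − 39/48 = 18.75%, or 150 per 800.

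**141 by month 18, then even to 800 by month 48** (659 women over 30 months)
- Randomised by month 27: 141 + 659 × 9/30 = 338.7. No 60-month score: 1 − 338.7/800 = 57.7%.
- Randomised by month 39: 141 + 659 × 21/30 = 602.3. No 48-month score: 1 − 602.3/800 = 24.7%.

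Even accrual would give 800 × 18/48 = 300 by month 18, so the protocol's own criterion allows a slower start and the larger shares.

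**If data are cut at exactly 36 months (month 84)**
- No 60-month score: 1 − 24/48 = 50% with even accrual. With the slower start, 141 + 659 × 6/30 = 272.8 women, so 1 − 272.8/800 = 65.9%.

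| Assumption | No 60-month score | No 48-month score |
|---|---|---|
| Even accrual, month 87 | 43.75% | 18.75% |
| 141 by month 18, month 87 | 57.7% | 24.7% |
| Even accrual, month 84 | 50% | 25% |
| 141 by month 18, month 84 | 65.9% | 33.0% |

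(The last two entries in the right-hand column use women randomised by month 36: 1 − 36/48, and 1 − (141 + 659 × 18/30)/800.)

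**Length of curve lost, even accrual, month 87.** For QLQ-C30/BR23, a woman short of 60 months has a last score at 36 months and loses 24 months of curve. The average loss is 0.4375 × 24 = 10.5 months. For EQ-5D and BREAST-Q, 18.75% lose 24 months and 43.75% − 18.75% = 25% lose 12 months. The average loss is 0.1875 × 24 + 0.25 × 12 = 7.5 months.

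**Timing if the analysis waits.** The last 60-month questionnaire falls at 48 + 60 = month 108. Adding 3 months gives month 111, which is 111 − 87 = 24 months after the section 16.6 analysis. No score is then missing through timing alone.

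**The case against.** Several points on the other side are sound.

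- *No bias between arms.* A reader might infer that mixing 36-, 48- and 60-month horizons distorts the comparison. The documents do not support that. Whether a woman reaches 60 months by the cut depends on her randomisation date, and both arms recruit concurrently at 1:2, so the mix should be the same in each. A repeated-measures model can handle this kind of missingness. A standardised AUC tolerates unequal follow-up, at the price of a less clearly defined quantity.
- *Precision.* A reader might take the missing shares as a direct measure of lost precision. That would hold only for a stand-alone contrast at 60 months in women who reached it, which the protocol does not plan. The planned methods use all earlier scores. With even accrual, mean follow-up capped at 60 months is still 55.4 months, although this counts calendar time and not completed questionnaires, for which the loss is larger.
- *One QALY or two.* A reader might infer that two conflicting QALY results would appear. Section 16.3 describes no QALY method and section 16.2.2 routes the QALY to section 9, so only one QALY calculation is described. The conflict is in stated timing. The project completion date is also not given; month 108 or later is inferred from the funded follow-up.
- *A deliberate 3-year minimum.* It is deliberate for local recurrence, and that timing is not questioned here. Reporting with staggered follow-up is normal.
- *Matters for the statistical analysis plan.* Section 16.3 leaves missing data and selection of subjects to that plan, and the AUC horizon may be settled there. The analysis date is different: section 16.6 itself fixes it.

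These points limit the consequences. They do not explain why the only quality-of-life analysis in section 16 precedes the end of its own data collection.

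**Conclusion.** The point holds as a timing fault affecting secondary outcomes only; neither primary outcome is touched. Section 16.6 as written leaves later recruits' scheduled and funded late scores out of the only planned quality-of-life analysis, and its wording does not agree with section 9.3 on when the QALY is analysed.

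At the section 16.6 analysis, about 44% of sub-study women could not yet have a 60-month score and about 19% could not have a 48-month score, assuming even accrual over 48 months and counting the 3-month lag. With the protocol's 141 by month 18 and even accrual after that, the shares are about 58% and 25%. A strict 36-month cut makes them larger. All these figures ignore deaths and questionnaire non-response.

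The cost is some precision and a shortened 5-year horizon for later recruits. The documents show neither a bias between arms nor two different QALY results.

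**What to change.** In section 16.6, keep the local recurrence analysis where it is and split off quality of life and the QALY. State that their final analyses take place 3 months after the last woman's 60-month questionnaire, on the same data cut as the economic analysis, and add a cross-reference in section 9.3. If quality of life is also reported at the 3-year cut, label it as an earlier report and fix the AUC horizon at 36 months for every woman.

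The cost is wording in two sections and one later analysis of questionnaires already scheduled within funded follow-up. The real downside is delay: the final quality-of-life result comes about 2 years later, which the labelled 36-month report would partly offset.
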